9.2 Setting

The study will be undertaken in Norway and will comprise all adult patients with NVAF who initiated treatment with either a NOAC or warfarin during the study period for the first time (OAC naïve first-time users). Study endpoints, discontinuation, switch to another OAC, death or end of study period will serve as censoring criteria.

The NVAF study population is defined in accordance with the 2018 European Heart Rhythm Association practical guide on the use of non-vitamin K antagonist oral anticoagulants in patients with atrial fibrillation, which define NOAC eligibility in NVAF patients as atrial fibrillation in the absence of rheumatic mitral stenosis or a mechanical heart valve.

Cohort 1 (registry study): Registries in Norway are nation-wide and provision of the information is mandatory, which eliminates the risk of both selection and re-call bias. The large and detailed dataset also makes it possible to adjust for other risk factors on which information is available.

In cohort 2, patients with NVAF diagnosis will be identified through extraction of patient-level data from EMRs from a number of hospitals in Norway, in order to describe these patients more closely regarding their clinical characteristics that are not available in nation-wide registers (e.g., in-patient treatments, anthropometric data and laboratory test results). This part of the

¹ Source: <http://www.legemiddelverket.no>

study is a pilot that will test the operational feasibility of accessing and linking the regional EMR data to the Norwegian Health Registers. Should the access to the regional EMR be granted, patients in cohort 2 will be identified and their EMRs extracted using the Pygargus Customized Extraction Platform (CXP). The extraction program has been used in a number of research projects since 2005 in the Swedish and Norwegian health care systems (6, 7). De-identified individual level data on age, gender, prescriptions, diagnoses, measures, laboratory tests, health care professional (HCP) visits, referrals, etc. can be collected from the EMRs into an encrypted database.

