9.3 Variables

9.3.1 Baseline characteristics

Table 4: Demography and clinical characteristics extracted for cohort 1 and 2

Variable	data source	Definition	Relevance
Age	FRG	Age in year	Co-variate and included in risk scores
Gender	FRG	Male or female	Co-variate and included in risk scores
Origin	FRG	Place of birth categorized as Norway, the Nordic countries, other Europe, rest of the world	Co-variate
Immigration date	FRG	Date of immigration out of Norway	Censoring
Emigration date	FRG	Date of emigration out of Norway	
Date of death	FRG	Date of death	Censoring and outcome variable
Alcoholism	NPR	ICD10 codes: E244, G312, G621, G721, I426, K860, O354, Z714, Z721, E52, K70, T51	Co-variate
Chronic kidney disease (CKD)	NPR	ICD10 code: N18 as an option 1 to define CKD Expanded list of codes to define CKD will be considered as an option 2, This list is being used for another ongoing study and is based on the approaches by Fleet et al (8)., Nielsen et al (9). and Weir et al (10). that in addition to identifying patients from the option 1 will allow an inclusion of patients with cystic kidney disease, unspecified kidney failure, chronic or unspecified nephritic syndrome, nephrotic syndrome, recurrent and	Co-variate

Variable	data source	Definition	Relevance
		persistent hematuria, nephropathy (diabetic, hypertensive, hereditary), chronic tubulo-interstitial nephritis, diabetes mellitus with kidney complications as having renal dysfunction (see Annex 3). The option 2 will be further clarified.	
End stage renal disease	NPR	ICD10 code: N185 or procedure codes KAGD40 (hemodialysis chronic) or KAS (renal transplant)	Co-variate Hemodialysis included in mHASBLED score
Congestive heart failure	NorPD	NorPD reimbursement codes for heart failure: I50 (ICD10) or K77 (ICPC) in ATC code group C	Co-variate. Included in CHA2DS2VASc score
Dementia	NPR	ICD10 codes F00-F04, G30	Co-variate
Diabetes	NorPD	ATC code A10A or A10B	Co-variate
Ischemic stroke	NPR	ICD10 codes: I63	Co-variate
Hemorrhagic stroke	NPR	ICD10: I60-62	Co-variate Included in mHAS-BLED score
TIA	NPR	ICD10 code: G45	Co-variate Included in CHA2DS2VASc score
Stroke&tia	NPR	ICD10: I60-I64	Co-variate Included in CHA2DS2VASc score
Thromboembolism	NPR	ICD10: I74	Co-variate

Variable	data source	Definition	Relevance
			Included in CHA2DS2VASc score
Hypertension	NorPD	Reimbursement codes in NorPD in ATC code group C: E10-E13, E15 (ICD10) or K86, K87 (ICPC)	Co-variate Included in mHASBLED and CHA2DS2VASc risk score

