9.5 Study size

There is no underlying hypothesis to confirm or reject. The sample is determined by eligibility. However it is desirable to assess the suitability of the available sample to produce useful estimates of the main outcomes.

The ratio of dispensations between the different NOACs and warfarin is estimated based on average number of dispensations in the period of 2014-2016 as given by NorPD statistics. Approximately half of patients treated with OAC have a dispensation for warfarin, 17%, 19% and 11% for apixaban, rivaroxaban and dabigatran respectively (Table 6). Based on previous studies, we estimate the risk of ischemic stroke and intracranial hemorrhage in the warfarin group, during an assumed mean follow-up of 18 months, to be 2.43% and 1.23% respectively.(1-4, 13-15)

ATC code and drug	2013	2014	2015	2016
	B01AA03- warfarin	87,994	77,755	69,289
B01AF02 – apixaban	2,260	8,640	21,507	37,276
B01AF01 – rivaroxaban	13,423	20,795	25,480	28,924
B01AE07 - dabigatran	13,879	15,358	13,843	13,327
Total	117,556	122,548	130,119	139,884

Table 6: Number of patients with at least one dispensation of an OAC annually in the period 2013 to 2016 as given by NorPD. The table gives the total OAC use for all indications.

The study population will comprise all adult OAC naïve NVAF patients in Norway who filled a prescription for an OAC (rivaroxaban, apixaban, dabigatran, warfarin) in the study period, defined as from 1 January 2014 to 30 June 2018 (or later depending on availability of data). Based on Table 6 demonstrating the total number of new prescriptions for OACs in 2013-2016 and based on a publication describing Norwegian NVAF patients, the sample size of naïve patients available for the study will be approximately 70,000 patients; however, as known from previous unpublished data, the proportion of naïve patients who get prescribed a NOACs is likely to be increasing in the last several years.

The tables below show the precision for the proportions and relative risks of ischemic stroke and intracranial hemorrhage that might be expected in terms of width of 95% confidence intervals.

Assuming that 90% of dabigatran, apixaban or rivaroxaban patients can be propensity score matched with patients treated with warfarin, the 95% confidence intervals for the matched proportions show a sufficient precision for ischemic stroke and intracranial hemorrhage (see tables below).

1:1 propensity score matched with warfarin			

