9.7 Data analysis

All data analyses will be performed using SAS statistical software version 9.4., and will be reported in a manner consistent with the Strengthening the Reporting of Observational Studies in Epidemiology (STROBE) guidelines.

Descriptive statistics will be used to present the data where continuous variables will be summarized as mean, standard deviation, median, minimum and maximum. Categorical variables will be described by frequencies and related percentages. Summaries will be reported separately for the elderly +75 years (cohort 1 and 2) and patients with renal impairment (cohort 2). Annual frequency of different OAC treatment during the study period in addition to adherence to each NOACs (high, moderate, low, and poor) will be presented. Also a separate analysis will be done to characterize patients with NVAf who have not been treated with OAC.

In the following, cohort 1 (registry) and cohort 2 (EMR) will be analyzed separately, but using the same analytical approaches.

The analyses will be performed on the total sample as well as on a confounder adjusted sample. It has to be kept in mind that analyses based on the overall sample (non-confounder adjusted sample) is prone to bias (see section 9.9).

Three separate propensity score models will be conducted and a 1:1 matching will be performed for:

- warfarin vs apixaban
- warfarin vs dabigatran
- warfarin vs rivaroxaban.

No matching to compare the NOACs among each other (e.g. apixaban vs rivaroxaban) will be performed due to underlying differences in prescribing preferences of different NOACs.

The propensity scores (PS) will be based on demographic variables and clinically relevant medical history, e.g. cardiovascular risk factors, comorbidities and concomitant medications at baseline.

Patients who switch or discontinue the OAC treatment will be censored at the date of switch or discontinuation. It cannot be ruled out that the switch of OAC (censoring) could be informative, but it is handled as uninformative censoring in the analyses.

Detailed methodology for propensity score modeling, matching, handling of missing data, summary and statistical analyses in this study will be documented in a Statistical Analysis Plan (SAP), which will be dated, filed and maintained by the sponsor. The SAP may modify the plans outlined in the protocol; any major modifications of primary endpoint definitions or their analyses would be reflected in a protocol amendment.

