9.7.1 Analysis of primary outcome(s)

The incidence rates and corresponding 95% confidence intervals for ischemic stroke and intracranial hemorrhage will be calculated for warfarin, apixaban, dabigatran and rivaroxaban cohorts on a confounder adjusted population.

The person time at risk will be calculated from first OAC use during the study period until a certain outcome, death or end of follow-up in June 30, 2018 (or later depending on the availability of data). The incidence rates will be calculated by the number of first cases of a certain event during the follow-up divided by person time at risk and will be presented per 100 (or 1000) patient years with exact 95% Confidence Interval (Poisson distribution) for all outcomes of interest, and separately for each OAC.

To compare outcomes of interest in cohorts of warfarin with apixaban, dabigatran and rivaroxaban users, the incidence rate ratios and corresponding 95% confidence intervals will be calculated.

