9.7.2 Further Analyses

The incidence rates and corresponding 95% confidence intervals for overall stroke (ischemic, hemorrhagic, other unspecified) and systemic embolism outcomes, myocardial infarction, all-cause mortality and major bleeding as defined by ISTH and the Cunningham algorithm (in a sub-set of patients; cohort 2) will be calculated for warfarin, apixaban, dabigatran and rivaroxaban cohorts.

Patients will be characterized according to demographic variables (age, gender), relevant medical history within 5 years prior to index date, different comorbidity risk scores (modified HAS-BLED, CHA2DS2VASC score, Charlson co-morbidity index), trends in OAC utilization from time of reimbursement, concomitant medications by OAC use and for NOACs-users, by the dose (standard or reduced) at start of follow up. Tests for differences between OAC sub-groups will be conducted using t-test, chi-square tests; the generalized linear model will be obtained to adjust for age and gender.

Additional analyses like a Cox proportional hazards regression models will be used to compare event rates of interest between the cohorts of users of different NOACs and warfarin adjusted for baseline covariates including age, gender, relevant medical history and concomitant medications. Hazard ratios with 95% confidence intervals for each study outcome will be presented (tables and Forest plots).

The occurrence of the first primary outcomes, as well as for the secondary outcomes among NVAF patients in warfarin versus NOACs will be described by Kaplan-Meier curves. The cumulative incidence of bleeding will be presented within different time windows (3m, 6m, 9m, 1 year, 2 years up until end of the follow-up).

Further details about the analysis and sensitivity analysis like Cox models evaluated within quintiles of PS probabilities can be found in the SAP.

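### Kaplan-Meier curves with death censored overstate the absolute risk of stroke, intracranial haemorrhage, myocardial infarction and bleeding; rates, rate ratios and hazard ratios are unaffected

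*Protocol*

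**What the plan says.** Section 9.7.2 names both the outcomes and the method. It covers the primary and the secondary outcomes, for warfarin against the NOACs, and says that their occurrence "will be described by Kaplan-Meier curves". The secondary outcomes in section 8.2 are overall stroke and systemic embolism, myocardial infarction, all-cause mortality and, in cohort 2, major bleeding.

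Death is handled the same way in three places:

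- Section 9.2: "Study endpoints, discontinuation, switch to another OAC, death or end of study period will serve as censoring criteria".
- Section 9.3.1, Table 4: date of death has the role "Censoring and outcome variable".
- Section 9.7.1: time at risk runs "until a certain outcome, death or end of follow-up in June 30, 2018".

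The sentence after the Kaplan-Meier sentence in section 9.7.2 reads: "The cumulative incidence of bleeding will be presented within different time windows". The windows run from 3 months to the end of follow-up, and no estimator is given. The one remark on informative censoring, in section 9.7, concerns a switch of anticoagulant, of which it says "it is handled as uninformative censoring in the analyses". No competing-risk method appears anywhere in the protocol.

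Section 9.3.4.1 also plans to analyse all-cause mortality alone and combined with stroke and systemic embolism. In those endpoints death is itself an event.

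**The concern.** A patient who has died cannot later have a stroke, an intracranial haemorrhage, an infarction or a bleed. Kaplan-Meier with death censored treats that patient as still able to have one, at the same rate as those who remain under observation. The resulting 1-KM is the risk in a hypothetical population without deaths. It is larger than the proportion of patients who experience the event, and the gap widens with mortality and with time.

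What is at stake is how absolute risk is read from the figures. If mortality differs between warfarin and a NOAC, the absolute risks are also inflated unequally. Mortality is clearly relevant here: it is a secondary outcome, section 7 describes the elderly as a large share of patients with atrial fibrillation, and follow-up can last about 4.5 years.

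**Working it through.** **Inputs from the protocol.**
- Section 9.5 puts the warfarin risks of ischaemic stroke and intracranial haemorrhage, "during an assumed mean follow-up of 18 months, to be 2.43% and 1.23% respectively".
- Mean follow-up is 18 months (section 9.2.1). The longest possible is 1 January 2014 to 30 June 2018, about 4.5 years.

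**Input assumed.** Mortality on treatment is not in the protocol. I use 5, 8 and 12% per year as the range.

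**The plan's own figures.** The dabigatran group size is 70,000 × 0.11 × 0.90 = 6,930. A proportion of 1.23% gives 85 events, with exact 95% limits of 0.98% and 1.51%, as in Table 9. A proportion of 2.43% gives 168 events, with limits of 2.08% and 2.81%, as in Table 7. Both reproduce. The protocol gives no figure for the Kaplan-Meier curves themselves.

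**Formulas, with constant hazards.** Let l be the event hazard, m the death hazard and t the time in years.
- 1-KM with death censored: 1 − exp(−l·t)
- Cumulative incidence with death competing: l/(l+m) × [1 − exp(−(l+m)·t)]

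**Intracranial haemorrhage.** 1.23% / 1.5 = 0.82% per year, rounded to l = 0.008. The rounding is why 1-KM at 18 months is 1.19% and not 1.23%.

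Worked case, t = 3 and m = 0.08:
- 1-KM = 1 − exp(−0.024) = 2.37%.
- Cumulative incidence = 0.008/0.088 × [1 − exp(−0.264)] = 2.11%.
- Relative excess = 2.37/2.11 − 1 = 12%.

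| Time | 1-KM | Cumulative incidence at m = 5 / 8 / 12% per year | Relative excess |
|---|---|---|---|
| 1.5 years | 1.19% | 1.15 / 1.12 / 1.09% | 4 / 6 / 9% |
| 3 years | 2.37% | 2.20 / 2.11 / 1.99% | 8 / 12 / 19% |
| 4.5 years | 3.54% | 3.17 / 2.97 / 2.74% | 12 / 19 / 29% |

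**Ischaemic stroke.** Here l = −ln(1 − 0.0243)/1.5 = 0.0164. With m = 0.08, 1-KM against cumulative incidence is 2.43% against 2.29% at 18 months and 7.11% against 5.99% at 4.5 years. The relative excess, 6% and 19%, is the same as for intracranial haemorrhage, because it depends almost entirely on m and t when events are rare.

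**Simulation check.** 400,000 patients were simulated with the stroke hazard above, mortality of 8 per 100 patient-years, and added administrative and discontinuation censoring. Kaplan-Meier gave 2.41% and Aalen-Johansen 2.27% at 18 months; at 4 years they gave 6.31% and 5.41%.

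**Unequal mortality.** For ischaemic stroke at 4.5 years, a group with 4 deaths per 100 patient-years has a relative excess of 9% (7.11% against 6.52%). A group with 8 has 19%. Both have the same 1-KM.

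**The case against.** The case against has several parts, and much of it limits the point.

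- **The primary analysis is safe.** It consists of incidence rates per person-time and rate ratios, with Cox models as additional analyses. Ending follow-up at death does not make any of these wrong. A reader might infer that the main comparison is biased; the protocol does not support that.
- **False separation of curves.** A reader might also infer that unequal mortality would create a spurious gap between the Kaplan-Meier curves. With equal event hazards the curves coincide whatever the mortality. What differs between drugs is how far each curve lies above the actual risk.
- **The excess is small where most follow-up lies.** At 18 months it is 0.04 to 0.10 percentage points for intracranial haemorrhage, well inside the Table 9 interval of 0.98% to 1.51%. Only patients who start on the first day of the study period reach 4.5 years. This stands, although a bias does not shrink as the sample grows.
- **Mortality is assumed.** This also stands. The direction is firm, the size is a range, and a difference between drugs is only a possibility.
- **The bleeding-window sentence names no estimator.** It is therefore not wrong as written; the most one can ask is that the estimator be named.
- **Subgroups.** Higher mortality in patients over 75 or with renal impairment would widen the gap, but section 9.7.2 does not promise curves in those strata. The cohort is all adults, with no age distribution given.
- **Death-inclusive composites.** Applying a competing-risk estimator to every outcome except mortality would be an error, because section 9.3.4.1 plans composites that include death.
- **The statistical analysis plan may change the method.** Section 9.7 allows this. But the protocol does not leave the matter open: it names the estimator and says that death is censored.

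**Conclusion.** The point holds for ischaemic stroke, intracranial haemorrhage, overall stroke and systemic embolism, myocardial infarction and major bleeding. Followed as written, section 9.7.2 together with section 9.2 and Table 4 gives curves whose 1-KM lies above the true cumulative risk. The relative excess grows from about 4 to 9% at the mean follow-up to 12 to 29% at the longest possible follow-up. These figures rest on constant hazards, on the protocol's warfarin risk, and on assumed mortality of 5 to 12% per year. The effect is confined to descriptive absolute risks. It is a minor point, worth correcting because the correction is easy.

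**What to change.** In section 9.7.2, replace Kaplan-Meier with Aalen-Johansen cumulative incidence curves, with death as a competing event, for every outcome that does not include all-cause death. State that the cumulative incidence of bleeding at the fixed time windows uses the same estimator. Keep Kaplan-Meier for all-cause mortality and for the section 9.3.4.1 composites that contain it.

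The cost is a sentence or two and minor extra programming in SAS. Date of death is already collected (Table 4), so no new data are needed. The change does not deal with informative censoring at switch or discontinuation, which remains a separate limitation.

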9.7.3 Missing data

Missing data is not expected to be significant, as NorPD and NPD are both high quality national registers. But if there are any missing values, typically registered as NA (not applicable) in the data

files, these will be reported for all variables. If missing values should occur, and judged to be random, then imputation (if possible) will be carried out. Alternatively, missing values will be categorized as own category in multivariate analysis.

9.8 Quality control

The data from NorPD and NPR are considered high quality register data, however, some quality checking and data cleaning will be done to check for reasonability and consistency of data, e.g. by cross-tabulation of patient characteristics compared to publically available data and so forth. QC will be further detailed in the SAP.

The EMR data extracted in cohort 2 will undergo extensive cleaning and QC before analysis can take place.

9.9 Limitations of the research methods

The strength of the study is that it retrieves data from mandatory and nationwide registries in a public health care system that covers all residents. As a result, the dataset will give us a complete picture of all hospitalizations and prescriptions dispensed nationwide for the entire study period. This complete coverage of data eliminates also selection bias and recall bias that is an apparent problem using other databases being based on selected hospitals, health insurance schemes, or self-reported questionnaires. On top of the nationwide registry data EMR data will give us deeper level phenotypic data such as laboratory values (INR, Hb), weight/height, smoking and alcohol abuse.

This study will measure drug exposure at the level of pharmacy dispensation and will have no information on patient's real OAC intake.

There is also a risk of misclassification related to coding errors of hospital admissions; however, for serious conditions like bleeding and stroke this unlikely a problem. Within the scope of the study a formal validation of the AF diagnosis in NPR will be performed against EMR.

Channeling bias (confounding by indication and severity) pertaining to newer drugs given to poor responding or more fragile patients compared to established drugs is a potential limitation. To mitigate this risk of bias we will use warfarin as reference category and also start the study period 1 January 2014, which will omit the first 6-12 months of NOACs use after reimbursement approval, i.e. when prescription patterns have not yet been established.

Estimates based on the overall population are prone to bias because the decision to give one treatment over the other depends on different baseline characteristics. Therefore any differences in the estimates for some treatment may be caused by the differences in the populations rather by the given treatment.

Due to the separate estimation of the propensity scores the population to compare warfarin vs apixaban may be very different from the population to compare warfarin vs rivaroxaban. Therefore no comparison between the NOACs among each other can be made.

Nonetheless, and although adjustment for a number of important and known baseline characteristics will be performed, some unmeasured and residual confounding related to prescribing behavior or patient characteristics cannot be fully accounted for.

